10.4 Markers

Markers will be measured repeatedly over time. Any patient with both baseline and at least 1 later measurement will be included in descriptions of each marker. Patients will also be classified for each marker based on whether the marker decreased by at least 30%, stayed with 30% of baseline, or increased by at least 30%. Currently there is no knowledge of how the planned PD, serum, and bone marrow markers may predict overall survival. Exploratory analyses described below will be performed on the continuous values of the markers, changes, in the markers as continuous measures, and the classification strategy described here.

16.3.3 Survival Analysis.

Overall (OS) and progression-free (PFS) survival will be calculated from the date of study enrollment and will include all enrolled patients. Survival analyses will be performed when 90% of patients have died or 2 years after the last patient has completed treatment, whichever comes first. Plots of all patients and subgroups identified by marker exploration (described below) will be presented using the methods of Kaplan and Meier.

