10.5 Primary Objective Exploration

Each marker will be tested individually using a Cox regression model to determine whether it is associated with overall survival. Markers measured on a continuous or ordinal scale will be included with their original units in the model. First, the baseline values will be used to determine if the baseline is associated with survival. Next we will calculate the percent change from baseline and use that as a continuous measure in the model. The ordered category of reduced by 30%, same, or increased by 30% grouping will be used in the model. Finally, all observed values of the marker will be included as a time-varying covariate in the Cox regression model. Since this is an observational study to identify potential usefulness of biomarkers in predicting overall survival, no formal adjustments for multiple testing will be needed for future trial planning. However, for publication, only markers with a significance level of ≤ 0.002 will be considered meaningful in predicting survival. This is based on a Bonferroni correction of approximately 25 markers of interest. Additional regression-tree style partitioning may be performed to identify potentially meaningful cutpoints for combinations of markers. Cutpoints will be examined together with demographic and medical status variables. This will be purely exploratory and will need to be confirmed in an independent data set in a future trial.

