10.8 Determination of Sample Size

This is an observational study of a new standard therapy with proven safety and efficacy to identify markers that change with treatment and are associated with overall survival. All findings will be preliminary and will be used to design future trials of scientific determination. No formal sample size criteria have been used. However, with 25 patients, we will have 80% power to detect a hazard ratio (HR) of 1.57 for a continuous biomarker as associated with survival at a 2-sided 5% significance level if the standard deviation of the biomarker is 1.25. With wider spread of the biomarker values, smaller HRs can be detected. For example, if the standard deviation is 1.5, then a HR of 1.45 could similarly be detected as significant.

11. Data and Protocol Management

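### The p ≤ 0.002 publication threshold in section 10.5 allows for about 25 markers, but each marker is tested against OS in four Cox forms and the plan does not say which form must meet it.

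*Combined protocol and SAP*

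**What the plan says.** Section 10.5 tests each marker individually in a Cox model for overall survival (OS), in four successive forms:

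1. the baseline value;
2. percent change: "Next we will calculate the percent change from baseline and use that as a continuous measure in the model";
3. the ordered category of fall, no change or rise, with cuts at 30%;
4. the time-varying value: "Finally, all observed values of the marker will be included as a time-varying covariate in the Cox regression model".

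On multiplicity, section 10.5 separates two uses of the results. For planning, "no formal adjustments for multiple testing will be needed for future trial planning". For publication there is a rule: "However, for publication, only markers with a significance level of ≤ 0.002 will be considered meaningful in predicting survival". The reason given is: "This is based on a Bonferroni correction of approximately 25 markers of interest".

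Section 10.4 also plans analyses of continuous values, changes and categories, and ranks none of them. Section 10.6 repeats similar analyses for PFS. The primary objective in section 2 covers both predictive and prognostic markers, and section 10.8 gives the aim as "to identify markers that change with treatment and are associated with overall survival".

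**The concern.** The divisor of 25 counts markers, whereas the plan runs four OS tests per marker. Each marker therefore has up to four p-values, and no sentence says which must be at or below 0.002, or whether one is enough. Two analysts following the text could publish different marker lists from the same data. If the choice of form is left until the results are known, it can be guided by them.

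The threshold is the only multiplicity control stated for the marker analysis, and it decides which markers are reported as the answer to the primary objective. A reader of the publication would take the word Bonferroni to mean about a 5% chance of any false claim. That holds for one form per marker; it is not assured across all four.

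The change forms add a second gap, because section 10.5 names no visit for them. Section 3 and the section 7.2 schedule both place marrow sampling at weeks 12 and 24. For plasma they differ: section 3 gives weeks 12, 16 and 24 after baseline, while section 7.2 lists correlative blood only at screening and week 24, as an optional procedure.

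**Working it through.** **Inputs.** Threshold 0.002, about 25 markers and four Cox forms (10.5); overall two-sided 5% level, 25 patients, HR 1.57 and SD 1.25 (10.8); marker lists (10.2 and section 3). The documents give no correlations between forms, so those below are assumptions.

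**The plan's figure.** 0.05/25 = 0.002, which reproduces the stated level.

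**One form per marker.** Bound: 25 × 0.002 = 5%. If independent: 1 − 0.998^25 = 4.9%.

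**Any of four forms, one test per form.** Tests: 25 × 4 = 100. Bound: 100 × 0.002 = 20%. If independent: 1 − 0.998^100 = 18.1%.

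**Correlated forms.** Assume independent markers and four normal test statistics per marker with common correlation r. The two-sided critical value at 0.002 is 3.090. Let p be the chance, found by numerical integration, that at least one of a marker's four statistics exceeds it. Family-wise error is then 1 − (1 − p)^25.

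| r (assumed) | p per marker | Over 25 markers |
|---|---|---|
| 0.5 | 0.00742 | 17.0% |
| 0.7 | 0.00650 | 15.0% |
| 0.9 | 0.00460 | 10.9% |

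**Marker count.** Section 10.2 lists 8 serum, 12 marrow and 7 PD entries, 27 in all. If only Ki-67, gamma H2AX and the cleaved PARP entry count as PD readouts, the total is 8 + 12 + 3 = 23. Urine NTx, in section 3 but not in 10.2, would make these 28 and 24. For m from 23 to 28, 0.05/m runs from 0.0022 to 0.0018, and the four-form bound 4 × m × 0.002 runs from 18.4% to 22.4%. So about 25 is a fair count, but the exact level needs a list.

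**Several visits (illustration).** Suppose both change forms were run at every section 3 visit. A plasma marker would have 1 + 3 + 3 + 1 = 8 tests and a marrow marker 1 + 2 + 2 + 1 = 6. With 8 plasma markers and 17 others treated like marrow, that is 64 + 102 = 166 tests, a bound of 33.2%.

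**Two named forms.** Bound at 0.002: 2 × 25 × 0.002 = 10%. For 5% across both: 0.05/50 = 0.001.

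**Power, using the formula that reproduces 10.8.** Power = Φ(√d × SD × ln HR − z), with 1.25 × ln 1.57 = 0.5638.

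- d = 25, two-sided 0.05: Φ(2.819 − 1.960) = 80%, which matches 10.8.
- The first trigger for analysis is 90% deaths: "Survival analyses will be performed when 90% of patients have died or 2 years after the last patient has completed treatment, whichever comes first". 90% of 25 is 22.5, hence 23 deaths.
- d = 23 at 0.002: Φ(2.704 − 3.090) = 35%.
- d = 23 at 0.001: Φ(2.704 − 3.291) = 28%.
- If the two-year limit comes first there may be fewer deaths. The documents give no count; at an assumed 20, power at 0.002 is Φ(2.522 − 3.090) = 28%.

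**The case against.** The strongest reply is that the study is exploratory. Section 10.5 calls it observational and waives adjustment for planning, section 10.8 uses no formal sample size criteria, and it adds: "All findings will be preliminary and will be used to design future trials of scientific determination". The threshold triggers no trial action. This stands as a limit on the consequence. It does not remove the gap, because the publication rule is introduced as an exception to the waiver and is presented as a Bonferroni correction.

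A second reply is that the forms ask different questions. A baseline value bears on prognosis, while a change or on-treatment value bears on response to treatment. Taking each form as its own family of about 25 markers is reasonable, and 0.002 then gives about 5% per family. This also stands, but the plan does not say that it reads the threshold this way. It is also a reason not to insist on a single form, since one form would leave part of the section 2 objective outside the rule.

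Third, the 20% is not free of assumptions. It needs 25 markers, one test per form and valid nominal p-values. The last is not assured for Cox models on at most 25 patients with markers in original units, and this qualifies the 5% figure as well.

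A reader might go further and infer that 0.002 is simply wrong and that 0.0005 (0.05/100) is required. The documents do not support that. The level is correct for one form per marker, and they do not say that any form may qualify.

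**Conclusion.** The point holds as an undefined decision rule, and the plan should settle it before analysis. The level of 0.002 gives about 5% family-wise error within one Cox form. If a marker may qualify through any of the four, the bound is 20%: 18.1% under full independence, and about 11% to 17% at assumed between-form correlations of 0.9 down to 0.5. These figures assume 25 markers, one test per form and valid nominal p-values; testing change at more than one visit raises the bound.

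A reader might infer that the trial's false-positive rate is 20%, or that its marker results are unusable. Neither follows. 20% is a ceiling under one reading of an ambiguous sentence, and the effect is confined to which markers a publication may call meaningful.

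**What to change.** Before analysis:

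- List by name the markers counted, m.
- Name the form or forms that govern the publication claim. Given the two-part objective in section 2, this can be one baseline form (prognostic) and one change or on-treatment form (response to treatment). Report each as its own family at 0.05/m, stating that error is about 5% per family and up to about 10% across the two. If 5% overall is wanted, use 0.05/(2m).
- For a change form, name the visit. Marrow offers weeks 12 and 24. For plasma, first reconcile section 3 with the section 7.2 schedule.
- Label the remaining forms and the PFS analyses descriptive.

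Possible wording: *For publication, a marker is called meaningful if p ≤ 0.05/m in the Cox model of OS on [baseline form] or on [change or on-treatment form, with visit if a change form], where m is the number of markers in [list]. Error is controlled at about 5% within each form and up to about 10% across both. Other forms and PFS are descriptive.*

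If no form is named, the plan and the publication should state that 0.002 controls error at about 5% per form and up to about 20% across the four.

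The cost is a few sentences and a marker list, with no added patients or samples. Effects seen only in an unnamed form become descriptive, so fewer true markers may be flagged than under the any-form reading. If a change form at a named visit is chosen, only patients sampled at that visit contribute. With 23 deaths and m = 25, power for HR 1.57 and SD 1.25 stays at about 35% at 0.002 and falls to about 28% at 0.001. Disclosure alone costs no power.

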10.6 Secondary Objective Analyses

Similar analyses as described for the primary objective will be carried out for progression-free survival as well. Graphical displays including individual biomarkers and progression events will be explored for patterns.

10.8 Determination of Sample Size

This is an observational study of a new standard therapy with proven safety and efficacy to identify markers that change with treatment and are associated with overall survival. All findings will be preliminary and will be used to design future trials of scientific determination. No formal sample size criteria have been used. However, with 25 patients, we will have 80% power to detect a hazard ratio (HR) of 1.57 for a continuous biomarker as associated with survival at a 2-sided 5% significance level if the standard deviation of the biomarker is 1.25. With wider spread of the biomarker values, smaller HRs can be detected. For example, if the standard deviation is 1.5, then a HR of 1.45 could similarly be detected as significant.

11. Data and Protocol Management

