10.2 Variables

Overall survival (OS):

OS will be measured as the number of months from enrollment until death. Patients who are alive at the time of database lock will be censored on the date of last contact.

Progression-free survival (PFS):

PFS will be measured as the number of months from enrollment until progression or death, whichever comes first. Patients who are alive and free of progression at their last response evaluation will be censored on that date. Progression will be defined by the standards set forth within PCWG2.

Demographic variables:

Age at enrollment, race, ethnicity, ECOG status, extent of bone disease (< 6, 6-20, >20)

PD Effects:

Tumor/osteoblast/osteoclast, Ki-67, gamma H2AX, cleaved PRP, cytokeratin/PSA, BALP, and TRAP

Serum biomarkers:

ALP, BALP, APG, RANKL, OPN, OC, CTX, PINP

Bone marrow biomarkers:

Alkaline phosphatase, osteocalcin, DMP, sclerostin, tenascin, periostin, lumican, decorin, osteopontin, osteonectin, nidogen-1, TGFb-induced protein ig-h3.

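### The 80% power in section 10.8 needs all 25 patients dead and a large-sample formula; at the 23 deaths of the 90% trigger the formula gives 76–77% and simulation about 65–67%

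*Combined protocol and SAP*

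**What the plan says.** Section 10.8 states that "with 25 patients, we will have 80% power to detect a hazard ratio (HR) of 1.57 for a continuous biomarker", "at a 2-sided 5% significance level if the standard deviation of the biomarker is 1.25". It adds a second example: "if the standard deviation is 1.5, then a HR of 1.45 could similarly be detected as significant". It names neither a formula nor a number of deaths. It also says that the sample size was not formally derived and that results are preliminary.

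Section 10.5 tests each marker singly in a Cox model for overall survival, and says that "for publication, only markers with a significance level of ≤ 0.002 will be considered meaningful in predicting survival".

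The timing is in the survival paragraph of section 10.4 (printed under the number 16.3.3): "Survival analyses will be performed when 90% of patients have died or 2 years after the last patient has completed treatment, whichever comes first". Section 10.2 adds: "Patients who are alive at the time of database lock will be censored on the date of last contact".

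**The concern.** In a Cox model the information about a marker comes from the deaths, not from the number enrolled. Section 10.8 quotes power for 25 patients, while section 10.4 plans to analyse before all of them have died. A sample of 25 is also small enough that a large-sample power formula may not hold.

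At stake is how a null result is read. Anyone who takes the 80% at face value will think a marker of the stated strength is missed one time in five. If true power is about two in three, it is missed about one time in three. Section 10.8 says the results will be used to design later trials, so a marker could be dropped on a mistaken view of what this study could see.

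**Working it through.** **Inputs.** From 10.8: N = 25, two-sided 5%, power 80%, HR 1.57 with SD 1.25, HR 1.45 with SD 1.5. From 10.4: 90% of 25 is 22.5, so the first limb of the trigger is met at the 23rd death.

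**Reproducing the plan's figure.** The large-sample formula for a continuous covariate is D = (1.960 + 0.842)² / (SD × ln HR)², where D is the number of deaths.

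- SD 1.25, HR 1.57: SD × ln HR = 0.564, so D = 24.7.
- SD 1.5, HR 1.45: SD × ln HR = 0.557, so D = 25.3.

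Solved for the HR at D = 25, it gives 1.566 and 1.453, which round to the two printed values. At D = 24 they would round to 1.58 and 1.46. So 10.8 treats 25 patients as 25 deaths.

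**Same formula at fewer deaths.** Power = Φ(√D × SD × ln HR − 1.960).

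| Deaths | HR 1.57, SD 1.25 | HR 1.45, SD 1.5 |
|---|---|---|
| 25 | 80.5% | 79.6% |
| 24 | 78.9% | 77.9% |
| 23 | 77.2% | 76.2% |
| 20 | 71.3% | 70.3% |

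**Simulation at the actual sample size.** The set-up was 25 patients, a normal marker, exponential survival with proportional hazards, a common time origin, follow-up ending at the D-th death, and 60,000 runs. Results are Wald / likelihood-ratio / score.

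| Deaths | HR 1.57, SD 1.25 | HR 1.45, SD 1.5 |
|---|---|---|
| 25 | 66.5 / 67.6 / 67.3% | 65.6 / 66.7 / 66.5% |
| 24 | 67.0 / 68.4 / 68.0% | 66.1 / 67.4 / 67.1% |
| 23 | 65.5 / 66.8 / 66.4% | 64.7 / 65.9 / 65.6% |
| 20 | 61.9 / 63.2 / 62.9% | 61.0 / 62.3 / 62.0% |

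The rows for 24 and 25 deaths differ only by simulation error, because the last death has a risk set of one and adds nothing to the partial likelihood.

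**Checks on the simulation.** Under no effect, the tests rejected 5.3–5.7% of the time at 23 deaths, so low power is not due to conservative tests. With 1,000 patients, all dead, and the effect rescaled so that the formula gives 80%, simulated power was 78%. The simulation therefore approaches the formula in large samples. Other marker shapes at 23 deaths gave 67–69% (uniform) and 61–66% (moderately skewed lognormal). Fixing the sample SD at the stated value gave 66–69%.

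**Where the shortfall comes from.** About 13 points are due to the formula at this sample size (80% to 66–68% with everyone dead). About 1 point is due to 23 rather than 25 deaths.

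**What 23 deaths can detect.** At two-sided 5%, HR 1.72 (SD 1.25) simulates to 79.0 / 79.9 / 79.6% and HR 1.57 (SD 1.5) to 78.7 / 79.8 / 79.4%. Per SD that is exp(1.25 ln 1.72) = 1.97 and exp(1.5 ln 1.57) = 1.97. The plan's stated effects are exp(1.25 ln 1.57) = 1.76 and exp(1.5 ln 1.45) = 1.75 per SD.

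**Publication threshold.** Section 10.8 claims no power at 0.002. For context, the stated HRs simulate to 17–22% there with 23 deaths.

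**The case against.** The strongest reply is that nothing depends on the figure. Section 10.8 disclaims a formal sample size basis, and no stopping rule or analysis uses the 80%. That limits the importance and stands. It does not make the number correct: the disclaimer covers why N is 25, and the power statement follows it without qualification.

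A second reply is that only 3–4 points follow from the plan's own text, since a large-sample formula is common practice and the simulated 65–67% needs assumptions the plan does not make. It is true that the exact value depends on marker shape. The direction does not: every shape tried at 23 deaths fell between 61% and 69%.

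A third point is that 23 deaths may itself be generous. The two-year limb may come first, and no accrual period is given. Take the 14.9-month median survival cited in section 1.4, exponential survival and 24 weeks (5.5 months) of treatment. With no accrual period, each patient is followed 29.5 months, so 25 × (1 − 2^(−29.5/14.9)) = 18.7 deaths are expected. Accrual uniform over 24 months raises this to about 21. On those assumptions the 23rd death usually does not come first. This stands, and it makes matters worse: simulated power for the stated HRs is about 59–63% at 19–20 deaths. It also means that any replacement figure at 23 deaths must say that fewer are possible.

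In the other direction, section 10.2 censors at database lock, so a death between trigger and lock would count and 23 is not a hard ceiling. That does not rescue the claim, because even 25 deaths give only 66–68%.

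**Conclusion.** The 80% is wrong as written. It rests on an unstated assumption that all 25 patients die and on a formula that overstates power at this sample size. At the 90% trigger, power for the stated effects is 76–77% by the plan's apparent formula and about 65–67% by simulation. The simulated figure assumes a normal marker and proportional hazards with 23 of 25 dead. If the two-year limit comes first, power is lower.

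This should be fixed, but it does not threaten the study. The design, sample size and analysis do not depend on the figure, and the plan presents its findings as preliminary.

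**What to change.** Reword 10.8 only. Keep its opening disclaimer, and replace the two power sentences with text such as:

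> The following figures assume 23 deaths, the number at which 90% of patients have died; fewer are possible if the 2-year limit comes first. By simulation (25 patients, normally distributed biomarker, Cox model), 23 deaths give about 80% power at a two-sided 5% level, unadjusted for multiplicity, to detect a HR of about 1.72 if the biomarker SD is 1.25, or about 1.57 if it is 1.5 (about 1.97 per SD).

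Two additions would help but are not required:

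- The values for 20 deaths, about 1.77 and 1.61. The 23-death HRs have only about 75–77% power at 20 deaths.
- The HRs with 80% power at the 0.002 level and 23 deaths, about 2.3–2.5 (SD 1.25) and 2.0–2.1 (SD 1.5), depending on the test.

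Do not simply put D = 23 into the large-sample formula. The resulting HRs (1.60 and 1.48 at 5%; 1.93 and 1.73 at 0.002) simulate to about 69–71% and 48–55%, not 80%.

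The cost is a short simulation and a few sentences. N = 25, the section 10.5 model and the analysis timing do not change. The stated detectable effects become less favourable.

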11.1 Registration Procedure and Data Reporting

All data will be entered to the Department of Genitourinary Medical Oncology Oracle database (GURU). GURU is a password protected database with an audit trail. Data can be collated with a unique GURU identification in order to de-link information. The minimum required fields will be entered to the MDACC required data collection systems (CORe/PDMS). Registration data entry will occur prior to initiation of therapy. All eligibility criteria must be satisfied. Reporting to the supporting agency will follow the contract agreement.

11.2 Clinical Trial Posting

Information related to this study will be posted on www.clinicaltrials.gov before the first patient is enrolled in the study.

